7.4.3 Selection of doses in the trial

The selected dose of 1 mg GlucaGen is the recommended dose for treatment of severe hypoglycemia. Based on pre-clinical and clinical studies, it has been demonstrated that 0.6 mg of dasiglucagon results in an initial pharmacodynamic response (i.e. acute glucose mobilization) comparable to 1 mg GlucaGen.

7.4.4 Treatment compliance

All trial medications will be prepared and administered by unblinded trial personnel.

7.4.5 Method of assigning patients to treatments or treatment sequences

Patients who meet all inclusion and none of the exclusion criteria and have given written informed consent will be randomized in a 1:1 ratio to either dasiglucagon or GlucaGen via an Interactive Web Response System (IWRS) that will assign a kit number to one of the 2 aforementioned treatment arms.

Patients with previous exogenous glucagon exposure will not be excluded from the trial, but the information on previous glucagon administration will be recorded, to enable subgroup analyses.

In the event of an emergency, e.g., when it becomes necessary for the investigator to know which treatment the patient is taking, the code for that patient can be broken by the investigator, preferably after consultation with the medical monitor. Emergency code breaks can be performed using the IWRS.

7.4.6 Blinding

This is a double-blind trial. Since dasiglucagon is available as a liquid formulation and GlucaGen is available as a powder for reconstitution, and they are therefore not identical in appearance, unblinded trial personnel will be responsible for handling, preparing, and administering the trial medication. To maintain double-blind conditions, all trial assessments at the trial site will be done by blinded trial personnel not involved in the administration of trial medications. However, exposure assessments and ADA assessments will be performed by unblinded personnel at the specialty laboratories, to make sure that dasiglucagon or GlucaGen administration is matched with the applicable bioanalytical assay.

7.4.7 Drug accountability and disposal

Handling, preparation and administration of trial medication will be done by unblinded trial personnel. Each center will keep accurate records of the trial supplies received, stored, and dispensed, using appropriate forms. The trial supplies will be stored under appropriate conditions, locked and with restricted access.

All unused supplies and all empty and partially empty containers of trial medication will be stored until the trial closure visit has been performed and then sent to the sponsor.

7.4.8 Prior and concomitant therapy

Prior glucagon exposure will be recorded in the eCRF at screening. All concomitant medications will be recorded in the eCRF at each visit.

Patients using any new concomitant medication resulting in fulfillment of a dosing day exclusion criterion will be excluded from the dosing visit, but can be rescheduled to one of the following days. Each dosing visit can only be rescheduled once. See Section 7.3.3.1 for possible reasons for patient discontinuation.

7.4.9 Treatment after end of trial

Not applicable in this trial.

7.5 Assessments and schedule of measurements (overview)

The following assessments and measurements will be carried out at the times specified in the trial flow chart (Table 2-1).

Informed consent will be obtained prior to any trial-related procedures; see Section 11.3.

7.5.1 Screening examination

At screening (Visit 1), the following assessments will take place:

- Informed consent
- Check of patient eligibility
- Demographics
- Body measurement
- Medical history
- History of alcohol/drug abuse
- Concomitant illnesses
- Prior medications
- Concomitant medications
- Physical examination
- Vital signs
- ECG
- AEs
- Hematology, biochemistry, coagulation
- Pregnancy test (women only)
- Urinalysis
- Urine drug screen (trial site testing)
- Alcohol breath test

7.5.2 Instructions to patients prior to dosing

On dosing days, patients are allowed to consume a small meal for breakfast with corresponding administration of rapid acting insulin to address the meal and in accordance with their normal management of blood glucose levels.

Use of long-acting insulin and rate of basal continuous subcutaneous insulin infusion (CSII) will be continued according to normal glycemic management of the individual patients during dosing days.

7.5.3 Procedures and assessments during the treatment period of the trial

At Visit 2 (Day 0) patient eligibility is rechecked (check of changes between the screening visit and Visit 2) and patients eligible to participate will be randomized to treatment with dasiglucagon or GlucaGen.

Additionally, during the treatment period of the trial, at Visits 2 and 4 (Days 0 and 14), the following assessments will take place:

- Concomitant medication
- Check of withdrawal criteria
- Check of dosing day exclusion criteria
- Vital signs (pre-dose, and at 30 and 90 min post-dosing)
- ECG (pre-dose, and at 30 and 90 min post-dosing)
- Local tolerability (at 0.5 and 2 h post-dosing)
- AEs
- Hematology and biochemistry (pre-dose, and at 30 and 90 min post-dosing)
- Urinalysis (pre-dose)
- Urine drug screen (pre-dose) at trial site
- Alcohol breath test (pre-dose)
- Dasiglucagon/glucagon plasma concentrations
(Pre-dose, 5, 10, 30, 60, and 90 min post-dosing. The actual time of blood sampling for exposure should not deviate from the nominal time by more than ± 1 min. Pre-dose is defined as within 5 min prior to dosing.)
- Plasma glucose concentration
(Pre-dose, 5, 10, 30, 60, and 90 min post-dosing. The actual time for blood sampling for plasma glucose should not deviate from the nominal time by more than ± 1 min. Pre-dose is defined as within 5 min prior to dosing.)
- Antibodies against dasiglucagon/glucagon (pre-dose)
- Administration of trial medication
Prior to administration of trial medication patients must reach a target plasma glucose level of 70-150 mg/dL. Plasma glucose levels may be adjusted by s.c. administration of a fast-acting insulin analog or by glucose ingestion. Patients must be fasting for 90 min after administration of trial medication, and can be treated individually to alleviate any potential side effects. See section 7.4.2. Patients will be observed for at least 5 h post-dose.

At Visit 3 of the treatment period (Day 7), only the following assessments will take place

- Concomitant medication
- Check of withdrawal criteria
- Check of dosing day exclusion criteria
- Local tolerability (at 0.5 and 2 h post-dosing)
- AEs

- Urine drug screen (pre-dose) at trial site
- Alcohol breath test (pre-dose)
- Antibodies against dasiglucagon/glucagon (pre-dose)
- Administration of trial medication
Prior to administration of trial medication patients must reach a target plasma glucose level of 70-150 mg/dL. Plasma glucose levels may be adjusted by s.c. administration of a fast-acting insulin analog or by glucose ingestion. Patients are NOT required to be fasting after administration of trial medication, and can be treated individually to alleviate any potential side effects immediately following dosing. See section 7.4.2. Patients will be observed for at least 5 h post-dose.

7.5.4 Follow-up period of the trial

After the final dose of trial medication (at Visit 4, Day 14, described above), patients will be followed up until Day 104 (Visit 7). During the follow-up period, visits take place at Days 35, 60, and 104 (Visits 5, 6, and 7).

At Visits 5 and 6 during the follow-up period, the following assessments will take place:

- Concomitant medication
- Check of withdrawal criteria
- AEs
- Antibodies against dasiglucagon/glucagon

Additionally, the following assessments will take place at Visit 5 only:

- Vital signs
- ECG
- Hematology and biochemistry

At Visit 7, the final visit of the follow-up period and of the trial (EoT visit), the following assessments will take place:

- Concomitant medication
- Physical examination
- Vital signs
- ECG
- AEs
- Hematology and biochemistry
- Urinalysis
- Antibodies against dasiglucagon/glucagon

7.5.5 Final examination at the end of the trial

The final visit of the trial is Visit 7 (Day 104 of the follow-up period; EoT visit). See Section 7.5.4 for further details.

7.5.6 Additional (safety) examinations

If there are any unclear symptoms or observations the responsible physician in charge may perform further medical examinations, other than outlined in this protocol, including further clinical laboratory tests, in order to clarify the relevance or to diagnose symptoms.

7.5.7 Safety laboratory tests

Samples obtained will be prepared and transferred to the appropriate laboratory by SynteractHCR according to Standard Operating Procedures. The parameters listed in Section 7.6.4.1 will be determined using standard methods.

The total volume of blood sampled per patient for safety analyses is 68 mL.

7.6 Immunogenicity, pharmacokinetic, pharmacodynamic, tolerability and safety measurements

Details of sampling for immunogenicity testing, plasma glucose concentrations, plasma trial medication concentrations, and safety laboratory testing are provided in a laboratory manual (see the Investigator site file).

7.6.1 Immunogenicity measurements

Antibodies against dasiglucagon/glucagon will be measured at all visits after screening. During the treatment period (Visits 2, 3, and 4) samples will be collected pre-dose.

The clinical ADA assays have been validated in accordance with existing guidelines and recommendations.^{6,7,8,9,10}

Confirmed positive anti- dasiglucagon antibody samples, (treatment-induced or treatment-boosted) from anti-dasiglucagon antibody-positive patients will be evaluated for binding titer neutralizing potential and titer as well as cross-reactivity towards endogenous glucagon.

No further serum sampling will be needed as the ADA samples can be used for Nab analysis.

The *in vitro* neutralizing effect of antibodies will be measured using an assay^{9,12} based on glucagon receptor transfected human embryonic kidney cells. The calculated sensitivity in previous studies was about 51.8 ng/mL. The assay was also validated for recombinant glucagon with similar results.^{11,12} In case of a positive result in the Nab assay, a titer estimation will be performed. The cell-based Nab analyses will be performed by a special laboratory, BioAgilytix, Durham, NC, USA.

In vivo neutralizing effect will be evaluated by comparing PK and PD endpoints between ADA positive and ADA negative patients, further investigation may be performed by correlating ADA titer with PK and PD endpoints.

Residual and additional antibody serum samples may be stored until approval of market authorization by the health authorities. Further characterization of the antibody response may be requested by the health authorities.

7.6.2 Plasma concentrations of dasiglucagon and GlucaGen

The exposure to trial medication (dasiglucagon or GlucaGen) will be assessed based on plasma concentration data ($AUC_{0-30\text{min}}$, $AUC_{0-90\text{min}}$, C_{max} , t_{max}) from samples collected at Visits 2 and 4 (after administration of the first and third doses of trial medication).

Samples will be collected pre-dose, and at 5, 10, 30, 60, and 90 min post-dosing. The actual time of blood sampling for exposure should not deviate from the nominal time by more than ± 1 min. Pre-dose is defined as within 5 min prior to dosing.

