10.1.4 Exposure and PD endpoints

Plasma dasiglucagon and glucagon concentrations 0-90 min from dosing: $AUC_{0-30\text{min}}$, $AUC_{0-90\text{min}}$, C_{max} , and t_{max} will be summarized with descriptive statistics.

Plasma glucose profiles 0-90 min from dosing: $AUE_{0-30\text{min}}$, $AUE_{0-90\text{min}}$, CE_{max} , and t_{max} will be summarized with descriptive statistics.

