5.1 Background of the trial

Hypoglycemia

Hypoglycemia in patients with diabetes is defined as episodes of an abnormally low plasma glucose concentration.¹ This is a common, unpredictable, and potentially dangerous side effect of treatment of diabetes mellitus with especially insulin or sulfonylureas. It is more frequent in patients with profound endogenous insulin deficiency, such as occurs in type 1 diabetes mellitus (T1DM) and advanced type 2 diabetes mellitus (T2DM). Treatment of T2DM with insulin causes hypoglycemia progressively and more frequently over time, whereas in T1DM, hypoglycemia is experienced throughout the course of established disease.

Symptoms and signs of hypoglycemia are not specific. Patients undergoing a hypoglycemic episode experience unpleasant symptoms such as anxiety, sweating, hunger, tremors, palpitations, paresthesia, nausea and pallor. Depending on its severity, the hypoglycemia may lead to mild confusion, behavioral changes, loss of consciousness, seizures, coma, and death.²

The incidence of hypoglycemic events or even the fear of hypoglycemia influences patients' adherence to prescribed treatment regimens for diabetes mellitus. This leads to inadequate glycemic control, which in turn may lead to an increased risk of diabetic complications.

Glucagon

Glucagon is a naturally occurring hormone, secreted from the alpha cells of the pancreatic islets. Glucagon plays a central role in the regulation of glucose homeostasis and is the counterpart of insulin for controlling blood glucose levels (i.e. it acts in opposition to insulin in terms of effects on blood glucose levels). Glucagon stimulates hepatic glycogenolysis and gluconeogenesis in hypoglycemic states, thereby restoring glucose homeostasis. Glucagon receptor agonism has also been shown to exert effects on lipid metabolism, energy balance, body adipose tissue mass and food intake. Insulin decreases blood glucose levels and cases of hypoglycemia can be reversed by glucagon. Therefore, glucagon is indicated for the treatment of severe hypoglycemia.

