Antibodies against therapeutic peptides like glucagon and analogues hereof may develop when injected subcutaneously. Although important, glucagon is not considered to have a critical endogenous function since other counter regulatory hormones are also induced during hypoglycemia (e.g. growth hormone, cortisol, and epinephrine). In addition, results from 3 mouse models defective in various pathways of the glucagon signaling have confirmed that glucagon action is dispensable for their development and survival. Also, in non-clinical toxicity studies performed with dasiglucagon (see below), no consequences of ADA formation have currently been observed. In summary, glucagon appears to have a partly redundant endogenous function. These non-clinical data are of importance when evaluating the consequences of ADA formation.

Dasiglucagon

Dasiglucagon (ZP4207) is a stable peptide analog of human glucagon, available in a ready-to-use liquid formulation and is in development for the treatment of severe hypoglycemia in insulin dependent patients with diabetes mellitus. Dasiglucagon is a specific and full glucagon receptor agonist designed to mimic the effects of glucagon, having a fast absorption and elimination (minutes). It is a peptide of 29 amino acids, with 7 amino acid substitutions compared to native glucagon. The main purpose of the substitutions is to increase the physical and chemical stability of the glucagon analog compared to marketed glucagon products such as Lilly Glucagon or GlucaGen®. Dasiglucagon exhibits improved physical and chemical stability and is available in an aqueous solution at neutral pH.³

Three clinical trials have been completed with dasiglucagon, a first human dose trial (ZP4207-14013), a multiple-dose dose-escalation trial (ZP4207-15007) to evaluate the safety, tolerability, pharmacokinetics (PK) and pharmacodynamics (PD) of dasiglucagon, and a phase 2 crossover trial to assess the pharmacokinetics and pharmacodynamics of a single dose of an optimized formulation of dasiglucagon administered subcutaneously (s.c.) in patients with T1DM (ZP4207-15126).³

Pharmacokinetics and pharmacodynamics of dasiglucagon

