5.2 Trial rationale

Dasiglucagon is in clinical development as a rescue treatment for severe hypoglycemia in patients with insulin-dependent diabetes mellitus. Immune responses to therapeutic peptides and proteins may develop after subcutaneous administration and could potentially adversely affect their safety and efficacy. The potential formation of high titer ADAs to dasiglucagon, although considered unlikely in a rescue indication, could influence the efficacy of dasiglucagon, either indirectly by interacting with the pharmacokinetics of dasiglucagon or directly by neutralizing the glucagon response.

In recent years, regulatory agencies have outlined and recommended the use of a risk-based approach in the evaluation and mitigation of immune responses to therapeutic compounds that may adversely affect their safety and/or efficacy. Both transient and persistent antibody response should be combined to determine the overall immunogenicity of a product. Persistent antibodies are of importance since patients with persistent antibodies could experience clinical adverse reactions affecting safety and efficacy, while a transient antibody response can resolve without further consequence.

The present trial aims to evaluate that immunogenicity risk with an assessment of the occurrence of ADAs and neutralizing ADAs, and of cross-reactivity with native glucagon, following repeated single doses of dasiglucagon by s.c. administration in T1DM patients. The trial further aims to evaluate the pharmacodynamics and pharmacokinetic responses and to correlate the consequence of an antibody response, if any, to pharmacodynamic and pharmacokinetic endpoints. The reference product in this trial is GlucaGen, a recombinant human glucagon approved for the treatment of the severe hypoglycemic reactions that may occur in the management of insulin-treated children and adults with diabetes mellitus. Given the differences in ADA assay for dasiglucagon and GlucaGen, a formal statistical comparison or non-inferiority testing is not performed.

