15. PHARMACOKINETIC (PK) AND PHARAMCODYNAMIC (PD) PROPERTIES

Pharmacokinetic and pharmacodynamic endpoints

Pharmacokinetic and pharmacodynamic characteristics are assessed by using the following endpoints:

1. Pharmacokinetics: Plasma dasiglucagon and GlucaGen® (glucagon) concentrations from 0-90 min after dosing will be evaluated based on the following endpoints: $AUC_{0-30\text{min}}$, $AUC_{0-90\text{ min}}$, C_{max} , t_{max} . Samples will be taken at visit 2 and visit 4 after first and third administration of trial medication. Samples will be collected pre-dose, and at 5, 10, 30, 60, and 90 min post-dosing.
2. Pharmacodynamics on plasma glucose concentrations after administration of first and third doses of trial medication. Samples will be collected pre-dose, and at 5, 10, 30, 60, and 90 min post-dosing:
 - Plasma glucose profiles over the period from 0-90 min after dosing will be evaluated based on the following endpoints: $AUE_{0-30\text{min}}$, $AUE_{0-90\text{ min}}$, CE_{max} , t_{max}
 - Achieving a plasma glucose increase of ≥ 20 mg/dL within 30 minutes after treatment

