16.2 Data handling

Serial blood samples for pharmacokinetic and pharmacodynamic assessments will be drawn at the following intervals: pre-dose and 5min \pm 1min, 10min \pm 1min, 30min \pm 1min, 60min \pm 1min and 90min \pm 1min after start of dosing.

Summary tables for raw plasma concentrations, evaluation of concentration versus time data:

- i.) *For all pre-dose samples, the sampling time will be set to zero.*
- ii.) *For post-dose samples, the planned sampling time will be used in summary tables and the actual sampling times will be used for all figures of individual concentrations*
- iii.) *All pre-dose concentration values $< LLOQ^{[1]}$ will be set to zero.*
- iv.) *Post-dose concentration values $< LLOQ$ after t_{max} will be set to zero if there are no further concentrations $> LLOQ$ at later time points.*
- v.) *Post-dose concentration values $< LLOQ$ after t_{max} will be set to the lower limit of quantitation if there are further concentrations $> LLOQ$ at later time points.*
- vi.) *Missing post-dose values will not be replaced.*

Determination of PK/PD metrics:

- i.) *For all pre-dose samples, the sampling time will be set to zero.*
- ii.) *For post-dose samples, the actual sampling time will be used.*
- iii.) *All pre-dose concentration values will be set to zero.*
- iv.) *Post-dose concentration values $< LLOQ$ before t_{max} will be set to zero if there are no further concentrations $> LLOQ$ at later time points.*

^[1] LLOQ: Lower Limit of Quantification

- v.) *Post-dose concentration values < LLOQ before tmax will be set to the lower limit of quantitation if there are further concentrations > LLOQ at later time points.*
- vi.) *Post-dose concentration values < LLOQ after tmax will be ignored if there are no further concentrations > LLOQ at later time points.*
- vii.) *Post-dose concentration values < LLOQ after tmax will be set to the lower limit of quantitation if there are further concentrations > LLOQ at later time points.*
- viii.) *Missing post-dose values will not be replaced.*

PK and PD metrics will be determined by SynteractHCR. Plasma concentration data will be transferred from external laboratory (York Bioanalytical Solutions (YBS), MLM laboratories) to SynteractHCR as detailed in separate data transfer specifications.

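### GlucaGen exposure metrics are derived from measured plasma glucagon with no pre-dose subtraction, so they may include the patient's own hormone

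*Protocol*

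**What the plan says.** Protocol 7.6.2 (same sentence in version 1 and in the current version): "The exposure to trial medication (dasiglucagon or GlucaGen) will be assessed based on plasma concentration data", taken at Visits 2 and 4, pre-dose and at 5, 10, 30, 60 and 90 minutes. SAP section 15 names the analytes: "Plasma dasiglucagon and GlucaGen® (glucagon) concentrations from 0-90 min after dosing will be evaluated".

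On the molecules, Protocol 5.1 says: "Glucagon is a naturally occurring hormone, secreted from the alpha cells of the pancreatic islets". Protocol 5.2 says: "The reference product in this trial is GlucaGen, a recombinant human glucagon". Of dasiglucagon, Protocol 5.1 says: "It is a peptide of 29 amino acids, with 7 amino acid substitutions compared to native glucagon". Protocol 7.4.6 has exposure samples run in an assay matched to the arm.

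On derivation, SAP 16.1 (Table 2) reads Cmax straight from the analytical data and defines AUC as the area under the concentration-time curve, with no baseline term. Table 3 in the same section defines the glucose AUE on a baseline-adjusted curve and CEmax as a change from baseline. SAP 16.2 has two rule lists. For the concentration summary tables, only pre-dose values below LLOQ become zero. For the metrics, rule iii has no such condition: "All pre-dose concentration values will be set to zero".

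Neither document subtracts endogenous glucagon from the PK metrics.

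**The concern.** An exposure metric should describe the drug that was given. In the GlucaGen arm the drug and the native hormone are both human glucagon, so a measured concentration may be the sum of the two. The plan draws a pre-dose sample that would show the endogenous part, but does not use it for correction.

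This matters for more than the exposure table. Protocol 7.6.1 judges in vivo neutralization by comparing PK and PD endpoints between ADA-positive and ADA-negative patients, and Amendment 2 added a dosing visit for ADA-positive patients to obtain those data. In the GlucaGen arm, changes in endogenous glucagon between visits or patients would be mixed into that comparison.

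**Working it through.** The plan states no figure on this point, so there is none to reproduce. The check puts a constant endogenous level b through the SAP's own rules and compares the result with the same profile free of b.

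**Inputs from the documents.** Sampling at 0, 5, 10, 30, 60 and 90 min; pre-dose set to zero; linear trapezoid ascending, logarithmic descending (SAP 16.1, 16.2). GlucaGen tmax 20 min and dasiglucagon half-life 28 min (Protocol 5.1).

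**Assumptions.** One-compartment profile; GlucaGen half-life 15, 28 or 40 min, because none is given; b expressed as a fraction f of the drug's own Cmax, because neither b nor a GlucaGen Cmax is given.

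**Step 1: what zeroing the pre-dose value removes.** By the linear rule, b alone contributes 5b/2 = 2.5b from 0 to 5 min (instead of 5b), then 25b up to 30 min or 85b up to 90 min.
- AUC0-30 keeps 27.5b of 30b = 92%.
- AUC0-90 keeps 87.5b of 90b = 97%.
- Cmax keeps all of b.

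The zero rule is therefore not a baseline correction. It trims one corner of the first trapezoid.

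**Step 2: one worked case, half-life 28 min.** C(t) is proportional to exp(-ke t) - exp(-ka t), with ke = ln2/28 = 0.0248 per min and ka = 0.0884 per min from ln(ka/ke)/(ka - ke) = 20. Scaled to a sampled maximum of 100, the values are 0, 59.4, 90.7, 100, 54.6 and 26.5.
- Without b: AUC0-30 = 148.5 + 375.25 + 1907 = 2431. Adding 30 x 45.4/ln(100/54.6) = 2251 and 30 x 28.1/ln(54.6/26.5) = 1166 gives AUC0-90 of about 5848.
- With b = 5 and pre-dose zero: 161 + 400.25 + 2007 = 2568. Adding 30 x 45.4/ln(105/59.6) = 2405 and 30 x 28.1/ln(59.6/31.5) = 1322 gives about 6295.
- Inflation: Cmax 105/100, +5%; AUC0-30 2568/2431, +5.7%; AUC0-90 6295/5848, +7.7%.

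**Step 3: the range over the three half-lives.**

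| f = b/Cmax (assumed) | Cmax | AUC0-30 | AUC0-90 |
|---|---|---|---|
| 0.1% | +0.1% | +0.1% | +0.1 to 0.2% |
| 1% | +1% | +1.1% | +1.4 to 1.7% |
| 5% | +5% | +5.6 to 5.7% | +7.0 to 8.6% |
| 10% | +10% | +11.3% | +14.0 to 17.2% |

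**Step 4: effect on comparisons.** Within the GlucaGen arm, an offset equal in ADA-positive and ADA-negative patients cancels in an absolute difference. In a ratio it does not: with b fixed at fraction f of the ADA-negative Cmax, a true Cmax ratio R appears as (R + f)/(1 + f), which is nearer to 1. Between arms, the midpoint of the earlier Cmax ratio interval is sqrt(0.8850 x 1.1991) = 1.030. If that were the true ratio and only GlucaGen carried the offset, it would appear as 1.030/(1 + f) = 1.020, 0.981 or 0.936 at f = 1, 5 or 10%.

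**The case against.** The strongest objection is that the size is unknown. The documents give no endogenous glucagon level, no GlucaGen Cmax in concentration units and no LLOQ. At f = 0.1% the effect on AUC0-90 is about 0.2%, and below LLOQ the subtraction does nothing. That stands, and it is why the conclusion is conditional.

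A reader might infer that the bias is certain and falls on GlucaGen alone. The documents do not support that. Assay specificity is not stated. The two assays are arm-matched, but Protocol 5.1 infers that the two peptides share epitopes, so cross-reaction of the dasiglucagon assay with native glucagon cannot be ruled out.

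A reader might also blame rule iii for the bias. Step 1 shows otherwise: zeroing slightly lowers AUC, and the cause is that nothing is subtracted.

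A third tempting inference is that rule iii hides antibody-bound dasiglucagon at the Visit 4 pre-dose sample, where seven days is 7 x 24 x 60/28 = 360 half-lives after the previous dose. This fails. A quantifiable value stays in Table 14.4.1.1 under the summary-table rules and in Listing 16.2.9.1. Restoring one as large as 10% of Cmax adds at most about 0.5% to AUC0-90 in the profiles above and nothing to Cmax. Assay cross-reaction would explain it as well as antibody binding. The rat AUC finding came after 13 and 26 weeks of treatment at about 8 mg/kg/day or more.

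Subtraction is also imperfect. Breakfast, insulin or glucose before dosing, and the hyperglycemia that dosing induces may all move the patient's own secretion within 90 minutes. That stands, and is a reason to show both sets of metrics. Finally, PK is descriptive and no between-arm ratio or test is planned, which limits the consequence.

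**Conclusion.** The point holds in conditional form. As written, the SAP derives GlucaGen Cmax and AUC from measured glucagon and makes no use of the pre-dose level. If that level is quantifiable, all of it stays in Cmax, about 92% of its area in AUC0-30 and about 97% in AUC0-90. The percentages in the table rest on an assumed constant b, an assumed fraction of Cmax and an assumed GlucaGen half-life. The dasiglucagon metrics escape only if their assay does not read native glucagon.

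Separately from the size of b, the two lists in SAP 16.2 disagree on pre-dose values. The metrics list is headed for PK and PD together, so read literally for glucose it contradicts the baseline-adjusted AUE and CEmax in SAP 16.1. That needs correcting in any case.

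The primary ADA incidence and the sample size of 45 per arm are unaffected.

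**What to change.** In SAP 16.2, limit metrics rule iii to pre-dose values below LLOQ. This matches the summary-table list and removes the conflict with the glucose metrics.

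For the GlucaGen arm, also derive Cmax, AUC0-30 and AUC0-90 after subtracting the same-visit pre-dose glucagon from each post-dose value. Report these beside the uncorrected metrics, and carry both into the ADA-positive versus ADA-negative comparison. State that constant-baseline subtraction is approximate. State too whether each exposure assay reads native glucagon, from its validation report.

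The cost is SAP wording, one more derived variable and a second set of GlucaGen metrics to present. No new samples are needed. Under SAP section 6, the same analysis added after database lock would have to be labelled post hoc.
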